### 5.5 Concomitant Medications

Other NSAIDs or glucocorticosteroids should be avoided or limited. Any use of systemic or topic NSAIDs or glucocorticosteroids should be clearly documented (time, doses, routes, indications) and followed regularly.

If a participant requires pain relievers or antipyretics, the use of non-NSAIDs, e.g., acetaminophen, should be encouraged. It is not necessary to break the blind in most situations. A protonic pump inhibitor (PPI, omeprazole 20 mg/day tablet) will be added during the period of any NSAIDs or glucocorticosteroids treatment and will be stopped once NSAIDs or glucocorticosteroids are withdrawn.

Short courses of systemic NSAIDs or glucocorticosteroids (defined as up to 2 weeks at a time) are allowed. No more than 1 month total of off-protocol NSAIDs or glucocorticosteroids is allowed in a 6 months period. If it is anticipated that continuous NSAIDs or glucocorticosteroids will be needed or if more than 1 month of NSAIDs or glucocorticosteroids occurs during a 6 months period, the participant will stop study drug. However, since the participant will still undergo his/her yearly scan, they can still be assessed in an intent-to-treat analysis and thus do not come off the study. Non systemic glucocorticosteroids use is allowed without time restrictions.

All medications (prescription and over-the-counter), vitamin and mineral supplements, and/or herbs taken by the participant will be documented on the concomitant medication CRF and will include: 1) start and stop date, dose and route of administration, and indication. Medications taken for a procedure (e.g., biopsy) should also be included.

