Controversy remains regarding the most appropriate long-term daily dose of aspirin in the prevention setting. The mechanisms by which aspirin reduces the risk of cancer are not clear. COX-2 is thought to be the isoform most commonly implicated in carcinogenesis, but at the low doses (80-325 mg), aspirin has little activity against this isoform^8. Aspirin is, in fact, 170 fold less effective at inhibiting COX-2 than COX-1. Nonetheless, aspirin may suppress the expression of COX-2, and it may also have antineoplastic effects that are unrelated to cyclooxygenase. Since the 81-mg dose and the 325-mg dose appear to suppress colorectal prostaglandin levels to a similar extent, we could postulate that the two doses may have equivalent potency through COX-related mechanisms. The major risk of aspirin, as with other NSAIDs, is the risk of bleeding. Although the antiplatelet effects of aspirin likely contribute to an increase in the risk of bleeding, as highlighted by an increased risk of hemorrhagic stroke of 0.2 events per 1000 patient-years, the majority of the increased bleeding has a gastrointestinal tract etiology. The influence of aspirin on gastric prostaglandin levels is dosage-dependent, with almost 50% inhibition at just 30 mg/d, but maximal inhibition requires approximately 1300 mg/d. Consistent with these data, all conventional dosages of aspirin are associated with an increased bleeding risk. In a clinical trial in which 1,121 patients with a recent history of histologically documented adenomas were randomly assigned to receive placebo (372 patients), 81 mg of aspirin (377 patients), or 325 mg of aspirin (372 patients) daily, the risk of bleeding was not a substantial problem and the risk of death and serious bleeding were similar among the groups. In a case-control study of patients admitted with gastrointestinal bleeding, the odds ratio (OR) for admission with a bleeding ulcer was increased among aspirin users regardless of dosage. Treatment with a 75-mg/d dosage of aspirin was associated with an odds ratio of 2.3 for a bleeding ulcer (95% CI, 1.2-4.4), whereas 300 mg/d increased the OR to 3.9 (95% CI, 2.5-6.3).

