## 4.2 Exclusion Criteria

4.2.1 Subjects with chronic treatment (at least twice/week for more than 3 months) with Aspirin or other NSAIDs.

4.2.2 History of allergic reactions attributed to compounds of similar chemical or biological composition to aspirin, NSAIDs, COX2 inhibitors.

4.2.3 Invasive malignancy (with the exclusion of basal cell carcinoma or skin squamous cell carcinoma) diagnosed during the last 2 years before randomization; stage I-II invasive malignancies that were diagnosed more than 2 years prior to randomization and have been treated curatively are allowed as long as all treatment is finished at least 18 months prior to randomization.

4.2.4 History of therapeutic doses of anticoagulants including warfarin and low molecular weight Heparin (e.g. for prior deep venous thrombosis and pulmonary embolisms) in the preceding year.

4.2.5 Uncontrolled intercurrent illness including, but not limited to, ongoing or active infection, symptomatic congestive heart failure, unstable angina pectoris, cardiac arrhythmia, or psychiatric illness/social situations that would limit compliance with study requirements.

4.2.6 Pregnant women are excluded from this study because Aspirin is an agent with the potential for teratogenic or abortifacient effects. Because there is an unknown but potential risk for adverse events in nursing infants secondary to treatment of the mother with Aspirin, breastfeeding should be discontinued if the mother is treated with Aspirin.

4.2.7 Individual may not be receiving any other investigational agents, antiplatelet agents (e.g. aspirin, clopidogrel (plavix or others)), anticoagulants (e.g. heparin or heparinoids, coumadin, or others), metotrexate, lithium.

4.2.8 Participants with bleeding diathesis, history of gastric/duodenal ulcers in the last 5 years, NSAID-precipitated bronchospasm, patients unwilling or unable to limit alcohol consumption to i.e.  $\leq 3$  alcohol drinks a day.

4.2.9 Participants who in the opinion of the PI will be at higher risk of ASA-related complications.

4.2.10 Participants with known inability to adequately absorb oral medication.

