### 5.4 Contraindications

Aspirin should not be taken by people who are allergic to ibuprofen or naproxen, or who have salicylate intolerance or a more generalized drug intolerance to non-steroidal anti-inflammatory drugs (NSAIDs), and caution should be exercised in those with asthma or NSAID-precipitated bronchospasm. Owing to its effect on the stomach lining, manufacturers recommend people with peptic ulcers, mild diabetes, or gastritis seek medical advice before using aspirin. Even if none of these conditions is present, the risk of stomach bleeding is still increased when aspirin is taken with alcohol or warfarin. Patients with hemophilia or other bleeding tendencies should not take aspirin or other salicylates. Aspirin is known to cause haemolytic anemia in people who have the genetic disease glucose-6-phosphate dehydrogenase deficiency, particularly in large doses and depending on the severity of the disease. People with kidney disease, hyperuricemia, or gout should not take aspirin because it inhibits the kidneys' ability to excrete uric acid, and thus may exacerbate these conditions.

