In case of concomitant medications, subjects are asked to contact the chemoprevention staff in order to check whether any potential interference is expected. Data on drug suspension or interruption will be reported into the CRFs.

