## **8.3 Off-Agent Criteria**

Participants may stop taking study agent for the following reasons: completed the protocol-prescribed intervention, adverse event or serious adverse event, inadequate agent supply, noncompliance, concomitant medications, medical contraindication. Participants will continue to be followed, if possible, for safety reasons and in order to collect endpoint data according to the schedule of events. Subjects will not be replaced.

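### Stopping study drug while staying on study is mandated only for NSAIDs and glucocorticosteroids (5.5); for an anticoagulant or non-aspirin antiplatelet started on study it is optional, and 8.4 and 6.9 can cost the month-12 CT

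*Combined protocol and SAP*

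**What the plan says.** Section 5.5 makes three provisions tied to particular drugs, and each names only NSAIDs and glucocorticosteroids.

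- A proton pump inhibitor "will be added during the period of any NSAIDs or glucocorticosteroids treatment and will be stopped once NSAIDs or glucocorticosteroids are withdrawn".
- A mandatory stop: "if more than 1 month of NSAIDs or glucocorticosteroids occurs during a 6 months period, the participant will stop study drug". The same applies if continuous need is anticipated.
- Retention: because the yearly scan still takes place, "they can still be assessed in an intent-to-treat analysis and thus do not come off the study".

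Other medications are only to be documented on the CRF.

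The protocol treats anticoagulants and antiplatelets as hazardous elsewhere. Section 4.2.7 excludes at entry anyone receiving "antiplatelet agents (e.g. aspirin, clopidogrel (plavix or others)), anticoagulants (e.g. heparin or heparinoids, coumadin, or others), metotrexate, lithium". Section 5.4 warns that "the risk of stomach bleeding is still increased when aspirin is taken with alcohol or warfarin", and 2.2 says that "the antiplatelet effects of aspirin likely contribute to an increase in the risk of bleeding".

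For medicines started on study, 5.7 has a contact step: "In case of concomitant medications, subjects are asked to contact the chemoprevention staff in order to check whether any potential interference is expected". It attaches no action. Section 8.3 lists concomitant medication and medical contraindication among the reasons for which a participant may come off agent, and adds: "Participants will continue to be followed, if possible, for safety reasons and in order to collect endpoint data". Section 8.4 allows off-study status by physician decision for non-compliance, concomitant medication or medical contraindication, and 8.3 already lists all three as off-agent reasons. Under 6.9, the site PI takes a participant who is unblinded before study completion off study.

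**The concern.** A drug considered risky enough to bar entry has no required action if it is started in month 2. A two-week NSAID course brings a mandated PPI. New warfarin or clopidogrel brings neither a mandated PPI nor a mandated stop, and the participant may stay on blinded tablets that could be aspirin.

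The second issue is endpoint capture. The primary endpoint is a 12-month change in millimetres, analysed by intention to treat. Section 5.5 protects that measurement for NSAID and steroid users. For everyone else, 8.3 points towards follow-up while 8.4 permits removal for the same reasons.

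The third issue is separate from concomitant drugs. Early unblinding leads to removal under 6.9, and the reasons given there include toxicity attributed to study agent and progressive disease. Month-12 values can therefore be missing for reasons tied to treatment or outcome.

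**Working it through.** **Reading the rules side by side**

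- *NSAID or glucocorticosteroid beyond the 5.5 limit:* the stop is mandatory, a PPI is given during use, and the participant stays on study.
- *Anticoagulant or non-aspirin antiplatelet started on study:* the stop is permitted (8.3), no PPI is tied to the drug, follow-up continues if possible (8.3), and off-study by physician decision is also open (8.4).
- *Early unblinding for any reason:* the participant is taken off study (6.9).

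The Early Termination column of the schedule of events shows no CT. Losing the month-12 scan after off-study is therefore an inference from the schedule; no rule states it. Cosmos participants have a yearly CT under their own protocol (2.3), but no text says that this scan is used once someone is off study. For participants recruited outside screening, no other yearly scan is named.

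When the final CT is missing, 13.4 places the participant in a failure group and 13.6 allows multiple imputation for variables with more than 5% missing. A failure label supplies no millimetre value for the planned t-test. Imputation supplies a modelled value, not a measured one. Since 5% of 128 is 6.4 participants, losses of 2-5% from this source alone would not exceed the imputation threshold.

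**Reproducing the plan's figure (13.3)**

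The inputs are a difference of 0.8 mm, SD 1.6 mm (effect size 0.8/1.6 = 0.5) and a two-sided two-sample t-test at alpha 0.05. The noncentral t solution is 63.77, rounded up to 64 per arm. Power at 64 per arm is 80.1%. The plan's 128 participants and 80% power are reproduced.

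**Size of the loss (assumed start rate of 2-5% in 12 months)**

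- Starts overall: 128 x 0.02 = 2.6 to 128 x 0.05 = 6.4.
- Starts per arm: 64 x 0.02 = 1.3 to 64 x 0.05 = 3.2, taken as 1 to 3.
- If all go off study without a month-12 CT and are left out: 63 per arm gives 79.5% and 61 per arm gives 78.2%.

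**Size of a possible bias (second assumption)**

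Suppose k aspirin participants are removed, each differing from the arm mean by 1 SD (1.6 mm) in the same direction, with nothing offsetting in placebo. The shift in the arm mean is k x 1.6/(64 - k).

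- k = 1: 1.6/63 = 0.025 mm, 3% of 0.8 mm.
- k = 3: 4.8/61 = 0.079 mm, 10% of 0.8 mm.

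**Cost of a mandatory stop (64 per arm analysed)**

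- No effect kept, k = 1: 0.8 x 63/64 = 0.788 mm, power 78.9%.
- No effect kept, k = 3: 0.8 x 61/64 = 0.763 mm, power 76.3%.
- Half the effect kept (stops spread evenly over the year, an assumption), k = 1: 0.8 x 63.5/64 = 0.794 mm, power 79.5%.
- Half the effect kept, k = 3: 0.8 x 62.5/64 = 0.781 mm, power 78.3%.

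**The case against.** The strongest reply is that the protocol already handles most of this. Staff ask about medications and adverse events at months 1, 3, 6, 9, 12 and 13, and participants are asked to call about new drugs. Medical contraindication is a listed reason to stop. Section 5.6 requires a stop for grade 2 events at least possibly related to study drug and for all grade 3-4 events, and a DSMB reviews toxicity. Leaving the decision to the treating physician is a defensible choice. This stands in part: participants are not unprotected. But 5.6 acts only after harm appears, and the contact steps bring the case to staff without saying what to do. The authors wrote a mandatory rule for NSAIDs and steroids, so they did not rely on discretion there.

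A reader might infer that nothing decides whether a participant who stops tablets stays in follow-up. The text does not support that: once drug is stopped, 8.3 says follow-up for endpoint data continues if possible. The weakness is that 8.4 offers an exit on the same grounds.

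A reader might also infer that starting an anticoagulant makes the missing data depend on treatment or outcome. The documents do not support this either. Such a start does not by itself trigger unblinding, which needs a request through the Protocol Chairman to the Task Order Monitor, or an emergency. The dependence on treatment or outcome comes from early unblinding under 6.9, whatever its cause.

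Finally, the power-loss and bias figures assume simple deletion, whereas 13.4 and 13.6 provide a failure group and imputation. They are illustrations, not predictions.

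**Conclusion.** The point holds as a cheap improvement that should be made; it is not a fatal flaw. Three things are established from the text. The mandatory stop and the explicit stay-on-study rule cover only NSAIDs and glucocorticosteroids. Section 8.4 repeats as off-study reasons three that 8.3 treats as off-agent reasons. Section 6.9 removes participants who are unblinded early.

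The effect on power is about 2 points at most under the assumed 2-5% start rate. The bias figure of 0.025-0.079 mm rests on a further, deliberately unfavourable assumption. The documents give no start rate and no figure for the combined bleeding risk. The case therefore rests on preventing an avoidable bleeding hazard that the protocol itself recognises, and on measuring the primary endpoint in everyone the intent-to-treat analysis is meant to cover.

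Methotrexate, lithium and open-label aspirin are outside this point.

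**What to change.** 1. **Section 5.5.** Add that if an anticoagulant or non-aspirin antiplatelet is started, study drug stops for as long as it is taken, without unblinding for this reason alone. The participant stays on study and has the month-12 CT. For a short prophylactic heparin course, tablets are interrupted and then resumed.
2. **Section 8.4.** Delete the three physician-decision reasons that duplicate 8.3. State that stopping study drug or starting a concomitant medication is not by itself an off-study reason.
3. **Section 6.9.** Replace off-study with off-agent. Follow-up and the month-12 CT continue where clinically appropriate and the participant consents, with no CT in pregnancy. The CT reader stays blinded.

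This is a short amendment to three sections. It needs no new data items, because concomitant medications and their start dates are already recorded. The price is that about 1-3 aspirin participants may stop tablets who would otherwise have continued, leaving power at 78.9-76.3% if they keep none of the effect, under the assumed rate. That cost arises only in comparison with continuing tablets alongside the new drug, since going off study would also end treatment. A few unblinded participants would remain in follow-up, which is why the reader's blinding needs to be written down.

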The actual identity of ld-CT detected GGO cannot be ascertained without histologic analysis, but this is the category of nodule that is most likely to represent atypical alveolar hyperplasia, the putative precursor of pulmonary adenocarcinoma. Kim et al. reported that of 53 persistent GGO in 49 patients who underwent resection, 68% proved to be bronchoalveolar carcinoma, 7.5% were adenocarcinoma with predominant bronchoalveolar components, 6% were atypical adenomatous hyperplasia, and 19% were nonspecific fibrosis or organizing pneumonia. Similarly, Ohtsuka et al. reported that of 26 patients who underwent resection, bronchoalveolar carcinoma was diagnosed in 10 patients (38%), atypical adenomatous hyperplasia was diagnosed in 15 patients (58%), and focal scar was seen in 1 patient (4%). Although criteria such as size, the presence of air bronchograms, and nodule sphericity on CT scan have been used to differentiate carcinomas from atypical alveolar hyperplasia, histological analysis remains the gold standard for definitive categorization of nodules and there continues to be debate regarding the overlap between small bronchoalveolar carcinomas and atypical alveolar hyperplasia. Since resected nodules represent lesions that are suspicious enough to merit surgery, it is possible and even likely that the smaller nodules identified in the context of our ld-CT screening study represent less advanced neoplasia than described in the above cited studies as well as non-neoplastic etiologies.

In 2010 we published the results of the Budesonide trial (MDA05-5-01), a randomized phase IIb study that evaluated the role of inhaled Budesonide in the shrinkage of CT detected undetermined lung nodules. The study showed an effect of the treatment only on non solid nodules and a trend in partially solid nodules. A 5-year follow up of the nodules with annual low dose CTs showed that the effect of treatment was maintained years after treatment and was significant for non solid and partially solid nodules (unpublished data). Specifically, after 60 months the mean reduction of maximum diameter in the treated arm were 2.65 mm and 0.69 mm in the non-solid and partially solid lesions, respectively.

We concluded that screen-detected non solid and partially solid nodules represent a good target to test chemopreventive agents and that the role of Budesonide deserves further investigation.

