## 13.2 Randomization/Stratification

In order to keep at minimum the imbalance in treatments a stratified blocked randomization strategy will be used considering only the relevant prognostic factors. Subjects will be stratified according to screening vs non screening CT scan, gender, smoking habits (current versus former smokers) and nodule type (non solid versus partially solid nodules). A blocked randomization will be done within each stratum. Other possible prognostic factors are age, the number of lesions, their volume doubling time and their size but since there is no evidence that they affect the response probability they will be included just in a stratified analysis, not during the randomization process.

Justification of stratification:

Stratification by nodule type and smoking status is planned because both non solid type and active smoking are associated with the risk of developing lung malignancies and their natural history, while stratification by screening vs non screening CT scan, and gender are conservative. The effect of aspirin has been variable in men and women for the prevention of certain conditions.

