## 13.3 Accrual and Feasibility

A sample size of 128 patients (64 per arm) achieve 80% power to detect a difference of -0.8 mm between the null hypothesis that both groups average reduction is -0.2 mm and the alternative hypothesis that the average reduction of target nodules in the aspirin group is -1.0 mm, with estimated effect size of 0.5 (common standard deviations of 1.6 mm) and with a significance level (alpha) of 0.05 using a two-sided two-sample t-test. The average shrinkage in the placebo arm is derived from the Budesonide trial.

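### No planned analysis accounts for inhaled steroids, although section 2.3 reports that inhaled budesonide had an effect on non-solid nodules; baseline use should be a covariate in 13.4

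*Combined protocol and SAP*

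**What the plan says.** Section 5.5 (Concomitant Medications) opens with a general instruction: "Other NSAIDs or glucocorticosteroids should be avoided or limited". It then caps systemic courses at two weeks each and one month in total per six months. It ends the topic with "Non systemic glucocorticosteroids use is allowed without time restrictions". The word inhaled does not appear, but inhaled use is non-systemic. The same section has every medication entered on the concomitant-medication CRF with dates, dose, route and indication. The Schedule of Events collects these data from the pre-study evaluation to month 13.

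Sections 4.1 and 4.2 name no corticosteroid. Section 13.2 says: "Subjects will be stratified according to screening vs non screening CT scan, gender, smoking habits (current versus former smokers) and nodule type". It adds age, lesion number, volume doubling time and lesion size for a stratified analysis, while stating that there is no evidence that they affect response. The primary test in 13.4 is a t-test without covariates. The models in 13.5 contain arm, visit, smoking history and age. Section 13.8 foresees no subgroup analyses.

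On the investigators' earlier trial of inhaled budesonide, section 2.3 reports: "The study showed an effect of the treatment only on non solid nodules and a trend in partially solid nodules". Section 13.3 relies on the same trial: "The average shrinkage in the placebo arm is derived from the Budesonide trial".

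**The concern.** The plan gives a stratified analysis to four factors that it says have no demonstrated influence on response. It gives none to the one co-treatment for which it cites randomised evidence on this type of nodule. That co-treatment is also the one freed from the time limits in 5.5. Participants are aged 50 or over with at least 20 pack-years, so some use of inhaled steroids is plausible, though the documents give no rate.

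If inhaled steroids shrink these nodules, users and non-users differ in mean change. That difference sits in the residual variance of an unadjusted t-test. If steroid users have less left to gain from aspirin, the treatment contrast is diluted. If use happens to differ between arms, or comes to differ after randomisation, the observed contrast shifts by an amount that no planned analysis would show. Section 13.3 contains no allowance for dropout, so the stated power has no reserve.

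**Working it through.** **Inputs from section 13.3.** "A sample size of 128 patients (64 per arm) achieve 80% power to detect a difference of -0.8 mm", "with a significance level (alpha) of 0.05 using a two-sided two-sample t-test", with a common SD of 1.6 mm.

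**Assumed inputs, not in the documents.** Proportion using inhaled steroids, p = 5 to 30%. Twelve-month effect of inhaled steroids on the per-person sum of diameters, b = 0.5 to 1.0 mm.

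**1. The plan's own figure.** SE = 1.6 × √(2/64) = 0.283 mm. Noncentrality = 0.8/0.283 = 2.83 on 126 degrees of freedom. Noncentral-t power is 80.1% at 64 per arm and 79.5% at 63, so the stated size reproduces. The smallest observed difference that reaches significance is about 0.56 mm.

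**2. Type I error.** With steroid use independent of arm, 40,000 simulated null trials per setting rejected in 5.0% (b = 1.0 mm, p = 20%) and in 4.8% even at an extreme b of 2.65 mm (p = 10% or 20%). There is no inflation.

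**3. Added variance.** Total SD = √(1.6² + b²·p(1−p)). For b = 1.0 and p = 0.30 this is √(2.56 + 0.21) = 1.664 mm. This assumes that the steroid variance comes on top of the 1.6 mm.

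| p | b = 0.5 mm: SD, power | b = 1.0 mm: SD, power |
|---|---|---|
| 5% | 1.604, 80.0% | 1.615, 79.4% |
| 10% | 1.607, 79.8% | 1.628, 78.8% |
| 20% | 1.612, 79.5% | 1.649, 77.7% |
| 30% | 1.616, 79.3% | 1.664, 77.0% |

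The loss is about 0 to 3 points.

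**4. Dilution, if steroid users gained nothing from aspirin.** The effect becomes 0.8 × (1−p). At p = 10% it is 0.72 mm and power is 70 to 71%. At p = 20% it is 0.64 mm, power is 59 to 61%, and 100 to 105 per arm would be needed for 80% (normal approximation). Nothing in the documents shows that this happens.

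**5. Chance imbalance at baseline.** SE of the difference in use = √(2p(1−p)/64). At p = 20% this is √(0.32/64) = 0.071. A 1.96-SE imbalance, which is about a one-in-twenty event, is 13.9 points. At b = 1.0 mm it shifts the arm difference by 0.14 mm. Conditional on that imbalance, type I error is about 7.8%.

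**6. Imbalance arising after randomisation.** A 10-point difference in use shifts the contrast by 0.05 to 0.10 mm, with type I error of 5.4 to 6.4%. The 10 points are purely illustrative.

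**The case against.** The strongest reply is that randomisation already deals with this. Chance imbalance in any baseline factor is part of the 5% error rate, and the simulation confirms it. A reader might infer that steroid use could mimic an aspirin effect and make a positive result unattributable. The documents do not support that as a systematic risk, and the same argument would apply to every unadjusted covariate in any randomised trial. This part of the reply stands.

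A reader might also treat inhaled budesonide as an established active drug on this trial's endpoint and insert the 2.65 mm from section 2.3, which would put power at 61 to 75% for 5 to 30% use. That figure, and the 0.69 mm for partially solid lesions, are unpublished 60-month reductions in maximum diameter in the treated arm alone. They are not placebo-subtracted 12-month differences in the per-person sum. The authors themselves say that the role of budesonide still needs study.

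A third inference is that steroid starts would be more frequent on aspirin through airway symptoms. Section 5.4 urges caution in asthma. But 4.1.1, 4.2.2, 4.2.8 and 4.2.9 remove symptomatic people, people with reactions to NSAIDs and those judged at higher risk. No excess rate is given anywhere.

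Two further points have weight. Criterion 4.1.5 requires nodules that persist for at least three months and allows at most 15% shrinkage of the largest, so long-term users enter with lesions that lasted despite treatment. And section 13.3 gives no source for the 1.6 mm SD, which may already contain steroid-related variance.

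What survives is the omission. A factor that the plan's own rationale reports as active on these nodules is recorded but never used. An adjusted analysis would sharpen the estimate and protect against imbalance in the one trial actually run.

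**Conclusion.** The point holds as an inexpensive improvement, not as a threat to validity. Overall type I error is intact. For assumed effects of 0.5 to 1.0 mm and use of 5 to 30%, the variance cost is about 0 to 3 power points. A rare baseline imbalance at 20% use would move the contrast by 0.14 mm per 1 mm of steroid effect, against a target of 0.8 mm. A material loss of power, to about 60% at 20% use, requires steroid users to gain nothing from aspirin, which is only a possibility. The true size cannot be fixed, because the documents give neither the rate of use nor a 12-month, placebo-adjusted steroid effect.

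The textual tension lies within section 5.5, between discouraging glucocorticosteroids in general and leaving non-systemic use without a time limit. A reader might see a contradiction between 5.5 and 2.3, but 2.3 sets no rule on co-medication. Which clinical rule should apply is not a statistical matter and is not judged here.

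**What to change.** - **Section 13.4.** Replace the unadjusted t-test with a per-subject linear model of the 12-month change in the sum of diameters. Include arm and baseline use of inhaled or other non-systemic airway glucocorticosteroids (yes/no, derived from the existing concomitant-medication CRF). At minimum, prespecify this as a supportive adjusted analysis. Settle the wording before unblinding.
- **On-study use.** Tabulate inhaled and systemic steroid use by arm over the 12 months. Do not exclude participants because they started or stopped after randomisation. That would condition on something treatment may have influenced and could itself introduce bias.
- **Stratification.** Leave 13.2 as it is. Four binary factors already give 2⁴ = 16 strata for 128 participants.
- **Section 5.5.** Reconcile the two statements on glucocorticosteroids so that sites read them the same way.

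The cost is one degree of freedom, one extra table and some wording; no new data are needed. The covariate removes the between-group variance and corrects for baseline imbalance. It does not recover power lost to dilution, and it does not correct for differences in use that arise after randomisation; the by-arm table would at least make those visible.
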